POPIA	Protection of Personal Information Act
pro-BNP	Prohormone brain natriuretic peptide
PSG	Polysomnography
PTSD	Post-traumatic stress disorder
QST	Quantitative sensory testing
RDW	Red cell distribution width
SAMRC	South African Medical Research Council
SAP	Statistical Analysis Plan
SARS-CoV-2	Severe acute respiratory syndrome coronavirus 2
SBIMB	Sydney Brenner Institute for Molecular Bioscience
SpO ₂	Peripheral oxygen saturation
TNF- α	Tumour necrosis factor alpha
TNFR1	Tumour necrosis factor alpha receptor 1
WHO	World Health Organization
WHO-DD	WHO Drug Dictionary
Wits	University of the Witwatersrand

SYNOPSIS

Title	A cross-sectional, observational study to characterise Long-COVID in an urban sample of South African adults
Short Title	ChaLoC
Background	
“Long-COVID” (also known as post-COVID-19 syndrome, post-acute sequelae of COVID-19, or chronic COVID syndrome, used here as ‘Long-COVID’ for brevity), is a complex array of postconvalescence symptoms following SARS-CoV-2 infection. The syndrome, common in COVID-19 survivors, can affect every organ system through as-yet uncharacterised but presumed immunological mechanisms. Prevalence depends on the definition used and time-period of follow-up, as well as the population being studied. The syndrome has been associated with significant and persistent disability in some survivors but has been hampered, until recently, by lack of a clinical definition, diagnostic criteria, and objective measures of disease or disability [1]. A Delphi-informed initial WHO clinical definition was released in early October 2021 but has attracted much criticism from both clinicians and survivors for a host of reasons, ranging from a lack of precision to a lack of inclusion [2].
 
Further complicating the syndrome is the context in which the SARS-CoV-2 epidemic occurred, which was associated with severe lockdowns in many countries (including South Africa) with social isolation, widespread fear and disinformation, widespread economic hardship, and loss of family and acquaintances, all of which contribute to symptoms (psychiatric and sleep disturbances, pain, and other syndromes) reported to be associated with Long-COVID. Finally, many Long-COVID symptoms overlap with those seen in patients hospitalised for any severe illness, especially those admitted to intensive care and ventilated. However, the proliferation of literature reporting associations of Long-COVID symptoms with more severe COVID-19 disease, and objective immunological, radiological, and organ-specific dysfunction in those reporting symptoms, suggests that the entity is real. The pathogenesis of Long-COVID is poorly understood, but this association with more severe disease - where immune dysregulation plays a major role in those with hospitalization, respiratory failure, and death - suggests an immune-mediated inflammatory dysfunction that may impact all organs [3-14].
 
The sheer rapidity of four major infection waves in South Africa, the initial focus on containing the hospital burden of those with severe illness, and subsequent emphasis on the roll-out of a mass vaccination program, has left little space for studying SARS-CoV-2 sequelae in survivors. This group, loosely and inaccurately termed “recovered” in South African reporting, were largely unvaccinated or partly vaccinated at the time of infection, leaving them at risk of developing Long-COVID.
 
Long-COVID reported symptoms are extraordinarily broad. Over 50 symptoms were reported in a recent review, with over 80% of COVID-19 survivors having at least one symptom after infection [4]. The diagnosis is one of exclusion, and symptoms may fluctuate although tend to resolve with time. It is unclear whether disability and organ damage may be permanent in some patients. No specific treatment exists, and interventions are typically symptom-directed. SARS-CoV-2 vaccination appears to benefit many symptomatic survivors [15]. At the time of writing, no African data characterising the clinical features of Long-COVID have been published.

Rationale	
Characterizing Long-COVID and related disability in local populations is an important first step to understanding the burden of morbidity and potential requirements of the health system in addressing symptoms and disability.
 
Almost all studies on Long-COVID have been undertaken in higher income countries, and largely in hospitalised patients, with almost no data emerging yet from Africa. This study aims to characterise Long-COVID in South African patients by leveraging an existing

	
patient base (including asymptomatic outpatients, symptomatic outpatients, hospitalised patients with severe COVID-19, and those who were vaccinated prior to widespread community exposure) and local research expertise.
 
The study is anticipated to add significantly to understanding Long-COVID, and to contribute African data to current efforts to develop syndrome diagnostic criteria (including the WHO case definition) and an understanding of the therapeutic needs of symptomatic survivors, thus informing South African health care.

Design	
This is a single centre, follow-up, observational, cross-sectional study of four distinct, longitudinal cohorts. Extensive clinical history will be obtained from each participant, and symptom questionnaire characterisation of Long-COVID (with a strong focus on organ-specific dysfunction, psychiatric, sleep, and pain parameters – all of which appear to be major features of Long-COVID), as well as laboratory and genetic characterisation will be performed. A subset of each cohort will be randomly selected for more specific syndrome characterisation related to sleep and pain, respiratory, cardiology, renal and glucose metabolism.
 
The consequences of Long-COVID will be described and compared in four large, well-described clinical cohorts of African patients surviving SARS-CoV-2:
 
• Cohort 1: asymptomatic subjects found to be PCR/antigen/antibody-positive during routine screening for SARS-CoV-2 infection• Cohort 2: symptomatic outpatients who were confirmed to have COVID-19 through a positive PCR/antigen test• Cohort 3: inpatients surviving hospitalisation for severe COVID-19 and who were PCR/antigen-positive• Cohort 4: participants vaccinated in clinical trials in 2020 prior to widespread community exposure to SARS-CoV-2, and hence protected from severe COVID-19 (and possibly Long-COVID) if subsequently infected. 
After obtaining informed consent from potential participants, a single cross-sectional, baseline visit will be conducted for each participant. Demographic data, clinical history (including COVID-19 history, targeted symptoms, and risk factors), COVID-19 vaccination dates (if administered), and details of previous and concomitant medications will be collected. Multiple questionnaires related to psychiatric screening, psychosocial factors, work function assessment, sleep quality, and pain assessment will be administered. Respiratory and cardiac function will be evaluated through a dyspnoea scale, walking test and an electrocardiogram (ECG). Laboratory evaluations will include a full blood count, serum chemistry, liver function tests, renal function assessment, inflammatory markers, and DNA extraction for genotyping. Blood and urine samples will be stored locally for possible future analysis. HIV testing will be performed for participants consenting to this optional assessment.
 
After the baseline visit, participants with Long-COVID will be identified using the WHO clinical definition and general health assessments [2]. Randomly selected sub-groups of participants with, and without, Long-COVID will be selected from each of the four cohorts for additional investigations through participation in the following sub-studies:
 
• Respiratory evaluation: dyspnoea assessment, high-resolution CT scan, lung function studies including spirometry and diffusion capacity (DLCO)• Cardiac evaluation: clinical history and examination, serial blood pressure, six minute walk test (distance), ECG, echocardiogram including speckle tracking, cardiac magnetic resonance imaging (MRI), creatine kinase MB fraction (CK-MB), cardiac troponin T (cTnT), prohormone brain natriuretic peptide (pro-BNP), and possible

	
coronary angiography in patients with acute coronary syndromes and unstable angina
 
• Psychiatric and neuroendocrine evaluation: questionnaires/surveys, semi-structured interview, home visit, saliva cortisol analysis, collection of diary data, actigraphy, adrenocorticotropic hormone (ACTH) challenge (cosyntropin sensitivity test [CST]), cellular immunity assessment• Sleep evaluation: questionnaires, actigraphy with sleep diaries, polysomnography• Pain evaluation: quantitative sensory testing (QST) and conditioned pain modulation (CMT) assessments• Glucose metabolism evaluation: oral glucose tolerance test (OGTT) including assessment of glucose, insulin, and c-peptide to estimate insulin sensitivity and beta-cell function [16]. 
Abnormalities detected in the assessments (including undiagnosed mental health issues) will be managed by on-study medical personnel with referral as appropriate.

Population	
Adults of at least 18 years of age with previous confirmed SARS-CoV-2 infection (symptomatic or asymptomatic) will be invited to participate.
 
The following eligibility criteria will be used to select study participants for the main study (baseline visit only):
 
• Inclusion criteria (baseline visit/main study):
1. Able and willing to provide written or electronic informed consent for the baseline visit prior to any study-specific assessment or procedure.2. Age at least 18 years at the time of signing the informed consent form.3. Previous asymptomatic SARS-CoV-2 infection, confirmed through a documented positive PCR, antigen, or antibody test, at least six months prior to the baseline visit [Cohort 1] or, previous symptomatic SARS-CoV-2 infection for which hospitalisation was not required, confirmed through a documented positive PCR or antigen test at the time, at least six months prior to the baseline visit [Cohort 2 only] or, previous hospitalisation for management and treatment of COVID-19 confirmed through a documented positive PCR or antigen test at the time, at least six months prior to the baseline visit [Cohort 3 only] or, previous asymptomatic or symptomatic SARS-CoV-2 infection, confirmed through a documented positive PCR, antigen, or antibody test, at least six months prior to the baseline visit and received a COVID-19 vaccine in a non-placebo arm of a COVID-19 vaccine study during 2020 [Cohort 4 only].4. Willing to consent to verification of vaccination status on the national Electronic Vaccination Data System (EVDS).5. Access to a reliable telephone or other device permitting information transfer.• Exclusion criteria (baseline visit/main study):
1. Symptomatic SARS-CoV-2 infection at any stage prior to the baseline visit [Cohort 1 only].2. Known SARS-CoV-2 infection, confirmed through a documented positive PCR test, prior to vaccination in a non-placebo arm of a COVID-19 vaccine study during 2020 [Cohort 4 only].3. COVID-19 within three months of the baseline visit.4. Personnel (e.g., investigator, sub-investigator, research assistant, pharmacist, study coordinator or anyone mentioned in the delegation log) directly involved in the conduct of the study.5. Any physical, mental, or social condition, that, in the Investigator's judgment, might interfere with the completion of the baseline assessments and

	
evaluations. The Investigator should make this determination in consideration of the volunteer's medical history.
 
6. Participant is judged by the Investigator to be at significant risk of failing to comply with the provisions of the protocol as to cause harm to self or seriously interfere with the validity of the study results.
 
Additional eligibility criteria will be used to identify study participants who are eligible for random selection for any of the sub-studies:
 
• Inclusion criteria (sub-studies):
1. Enrolled into main study and completed baseline visit.2. Able and willing to provide written or electronic informed consent for the relevant sub-study.• Exclusion criteria (sub-studies):
1. Pregnant women [Respiratory sub-study only].2. Current or previous smokers [Respiratory sub-study only]; refer to Respiratory Sub-Study Plan for definition of "previous".3. A well-characterised history of household exposure to biomass fuel used in the dwelling for heating and/or cooking, which preceded the acute COVID-19 illness [Respiratory sub-study only].4. A well-characterised underlying comorbid respiratory illness being treated on a continuous basis, which preceded the acute COVID-19 illness [Respiratory sub-study only].5. A well-characterised history of having had tuberculosis, appropriately diagnosed and treated, prior to the acute COVID-19 illness [Respiratory sub-study only].6. A history of diabetes and/or use of treatment for diabetes mellitus (Type 1 or 2) prior to COVID-19 or asymptomatic SARS-CoV-2 infection [Glucose metabolism sub-study only].7. Current, known diabetic or on treatment for diabetes mellitus (Type 1 or 2) [Glucose metabolism sub-study only].								
	Participants may be enrolled into more than one sub-study.								
Treatment	No treatment will be administered during this observational study.								
Objectives and Endpoints	

Primary Objective	Primary Endpoint	

To characterise Long-COVID in four cohorts of patients with previous SARS-CoV-2 infection (asymptomatic, symptomatic, severely symptomatic requiring hospitalisation, and those who were vaccinated prior to widespread community exposure).	Incidence, severity, and duration of Long-COVID symptoms.	

Secondary Objectives	Secondary Endpoints	

To describe the following characteristics in four cohorts of patients with previous SARS-CoV-2 infection (asymptomatic, symptomatic, severely symptomatic requiring hospitalisation, and those who were vaccinated prior to widespread community exposure):		

	Primary Objective	Primary Endpoint	To characterise Long-COVID in four cohorts of patients with previous SARS-CoV-2 infection (asymptomatic, symptomatic, severely symptomatic requiring hospitalisation, and those who were vaccinated prior to widespread community exposure).	Incidence, severity, and duration of Long-COVID symptoms.	Secondary Objectives	Secondary Endpoints	To describe the following characteristics in four cohorts of patients with previous SARS-CoV-2 infection (asymptomatic, symptomatic, severely symptomatic requiring hospitalisation, and those who were vaccinated prior to widespread community exposure):	
Primary Objective	Primary Endpoint								
To characterise Long-COVID in four cohorts of patients with previous SARS-CoV-2 infection (asymptomatic, symptomatic, severely symptomatic requiring hospitalisation, and those who were vaccinated prior to widespread community exposure).	Incidence, severity, and duration of Long-COVID symptoms.								
Secondary Objectives	Secondary Endpoints								
To describe the following characteristics in four cohorts of patients with previous SARS-CoV-2 infection (asymptomatic, symptomatic, severely symptomatic requiring hospitalisation, and those who were vaccinated prior to widespread community exposure):									

	
• Inflammatory markers• Psychological profiles• Psychosocial exposures• Work performance in employed participants• Sleep quality and disorders• Pain experience• Cardiorespiratory function• Standard laboratory parameters• Renal function• Host genetic factors that may be associated with Long-COVID	
• High sensitivity C-reactive protein (hs-CRP)• Interleukin-1β (IL-1β)• Interleukin-6 (IL-6)• Interleukin-8 (IL-8)• Tumour necrosis factor alpha (TNFα)• Tumour necrosis factor alpha receptor-1 (TNFR1)• Monocyte chemoattractant protein-1 (MCP-1)• Headache Impact Test-6• Patient Health Questionnaire-9• Generalised Anxiety Disorder 7• PTSD Checklist for DSM-5 - Civilian Version• Mood Disorder Questionnaire• Montreal Cognitive Assessment• Daily Fatigue Impact Scale• COVID-19 related stress questionnaire• Multidimensional Scale of Perceived Social Support• Perceived Stress Scale• Adverse Childhood Experiences tool• Normal activities and work productivity questionnaire• Pittsburgh Sleep Quality Index• Epworth Sleepiness Scale• Berlin Questionnaire for risk of sleep apnoea• International Restless Legs Syndrome Severity Scale• Sleep quality and mood visual analogue scale• Brief Pain Inventory• Modified Medical Research Council Dyspnoea Scale• Six-minute walk test (distance)• ECG parameters and morphology• Full blood count• Serum chemistry• Liver function tests• Glucose, HbA1C• Creatinine clearance• Cystatin-C• Urine dipstick parameters• Urine albumin-to-creatinine ratio• Genotyping results• DNA sequencing results
--	---	---

	
Exploratory Objectives
 
• The association between various specialised respiratory, cardiac, psychiatric and neuroendocrine, sleep and inflammation, pain, and glucose metabolism parameters and Long-COVID symptomatology will be explored in patients with Long-COVID from four cohorts of participants previously infected with SARS-CoV-2 compared to those with no signs or symptoms of Long-COVID (controls) from the same cohorts.
Sample Size	
One hundred (100) participants will be enrolled into each cohort (400 participants overall).
 
Enrolled participants with and without Long-COVID will be assessed for their suitability for various sub-studies. From the eligible participants, up to 30 from each cohort will be randomly selected to participate in each sub-study (while ensuring the requisite ratio of participants with Long-COVID to those without is maintained as applicable for each sub-study). The same participant may participate in more than one sub-study.
 
No formal sample size calculation was performed for this observational study.

Duration	
The duration of participation for each participant will either be a single visit (of approximately 6 hours), or two or more visits depending on whether they are enrolled into any sub-studies.
 
Participants selected for the sleep study will have an overnight admission at the Wits Faculty of Health Sciences sleep laboratory.
 
Enrolment to the study is expected to complete within one year.

Statistical Analysis	
Participants enrolled in the main, and various sub-studies, will be summarised. Demographic data and other baseline characteristics will be summarised overall, per cohort, and per disease status (Long-COVID or no Long-COVID) as relevant.
 
All primary and secondary endpoints will be summarised descriptively overall, per cohort, and per disease status (Long-COVID or no Long-COVID) as relevant, and for various risk factors as deemed appropriate in this exploratory study. Associations between outcomes, COVID-19 history, vaccination status prior to and since infection, and COVID-19 risk factors for severe disease will be explored. Co-factors such as time since initial SARS-CoV-2 infection, and possible confounders such as vaccination, exposure to potential disease-modifying repurposed drugs, and undisclosed vaccination or prior infections, will be accounted for as relevant.
 
Raw genetic genotyping results will be quality controlled by experienced SBIMB bio-informaticists. Association and fine-mapping will be used to investigate links between host genetics and Long-COVID variables generated by the broader study.

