5.4 Sub-Study Eligibility Criteria (Subsequent Optional Visit(s))

The following additional eligibility criteria will be used to identify study participants who are eligible for random selection for any of the sub-studies. Participants may be enrolled into more than one sub-study.

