7.1.2.2 Medical and surgical history

In addition to general information related to past and current relevant medical conditions and surgical procedures, and menstrual cycle, pregnancy and lactation status (for female participants only), the following specific information will be collected:

- COVID-19 history (for participants with previous symptomatic infection(s)) including:
 - Symptoms experienced (including cough, fatigue, fever, malaise, shortness of breath, ageusia, anosmia, and other symptoms)
 - Whether or not the participant was pregnant at the time of SARS-CoV-2 infection (female participants only)
 - Whether or not the participant required supplemental oxygen at the time of COVID-19
 - Whether or not the participant required intensive care unit (ICU) admission for COVID-19 (Cohort 3 only)
 - Whether or not the participant required mechanical ventilation for COVID-19 (Cohort 3 only)
- Long-COVID symptom-directed history to gather information about symptoms not assessed through the detailed questionnaires and surveys listed in Sections 7.1.2.5 to 7.1.2.6.

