7.1.2.8 Laboratory assessments

Blood sampling will be performed to collect samples for the following laboratory assessments:

- Full blood count: red cell count, haemoglobin, haematocrit, mean cellular volume (MCV), mean corpuscular haemoglobin (MCH), mean corpuscular haemoglobin concentration (MCHC), red cell distribution width (RDW), white cell count and differential (neutrophil count, lymphocyte count, monocyte count, eosinophil count, and basophil count), and platelet count
- Serum chemistry: serum sodium, potassium, chloride, bicarbonate, calcium (corrected), magnesium, phosphate, urate

- Liver function: total protein, albumin, total bilirubin, direct bilirubin, alkaline phosphatase (ALP), gamma-glutamyl transferase (GGT), alanine aminotransferase (ALT), aspartate aminotransferase (AST), lactate dehydrogenase (LDH)
- Renal function: urea, creatinine, estimated creatinine clearance (Cockcroft-Gault method), cystatin C
- Glucose metabolism: serum glucose, HbA1C
- Inflammatory markers: a multiplex cytokine panel will be run using Luminex technology at the Wits School of Physiology. Markers investigated will include hs-CRP, IL-1 β , IL-6, IL-8, TNF- α , soluble TNFR1, and MCP-1, but additional inflammatory markers may be included based on emerging reports in scientific literature
- DNA extraction for genotyping and sequencing at the Sydney Brenner Institute for Molecular Bioscience (SBIMB)
- HIV testing for participants consenting to this (optional).

A urine sample will be collected for:

- urinalysis via urine dipstick
- determination of the urine albumin-to-creatinine ratio
- pregnancy test for woman of reproductive potential.

Additional blood (50 mL) and urine (100 mL) samples will be stored for possible future analysis.

Details regarding blood and urine sample collection, handling and processing, and the assays (where applicable) will be documented in the Laboratory Manual.

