7.2 Sub-Studies

Participants may be invited to take part in more than one sub-study, or none. Up to 30 participants from each cohort will be enrolled into each sub-study. Participants with and without Long-COVID will be age- and gender-matched where possible.

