7.2.2.3 Psychiatric and neuroendocrine evaluation

Participants who are selected and provide consent for participation in the psychiatric and neuroendocrine sub-study, will have the following additional assessments performed:

- Repeated administration of questionnaires related to the psychological impact of COVID-19
- 4-day home collection of cortisol samples, sleep measurements and diary data
 - Serial collection of passive drool saliva samples for evaluation of cortisol concentrations
 - Objective measurements of sleep timing and quality through a wearable, accelerometry device (actigraphy)
 - Morning and evening daily diary completion to collect data related to sleep quality, health behaviours and stressors
- ACTH challenge (CST)
- *Ex vivo* cell culture analysis to evaluate cellular immunity through assessment of leukocyte inflammatory responses to a microbial challenge
- Semi-structured interview to assess perceptions of, and experiences related to, COVID-19

- A home visit to further understand the lived experience of long-COVID.

Further details can be found in the Psychiatric and Neuroendocrine Sub-Study Plan.

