7.2.2.6 Glucose metabolism evaluation

Participants who are not known diabetics, are not on treatment for diabetes mellitus (Type 1 or 2), and who have no history of diabetes or receiving treatment for diabetes mellitus (Type 1 or 2) prior to COVID-19 or asymptomatic SARS-CoV-2 infection, will be randomly selected for participation in the glucose metabolism sub-study. Those who provide consent for participation will attend a single visit where an OGTT, including measures of glucose, insulin, and c-peptide to estimate insulin sensitivity and beta-cell function, will be performed [16].

Further details can be found in Glucose Metabolism Sub-Study Plan.

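### Pregnancy is excluded from the respiratory sub-study only, so pregnant women can enter the OGTT and cortisol comparisons as cases or controls: a minor, cheaply closed gap

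*Protocol*

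**What the plan says.** The synopsis (sub-study exclusion criterion 1) reads "Pregnant women [Respiratory sub-study only", and Section 5.4.2 repeats the same restriction. Section 5.4 explains what the list is for: "The following additional eligibility criteria will be used to identify study participants who are eligible for random selection for any of the sub-studies". The main-study criteria in Sections 5.3.1 and 5.3.2 do not mention pregnancy.

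For the glucose metabolism sub-study, criteria 6 and 7 deal with diabetes and its treatment. Section 7.2.2.6 restates the pool in the same terms, saying that those who meet them "will be randomly selected for participation in the glucose metabolism sub-study". The outcome is an OGTT, "including measures of glucose, insulin, and c-peptide to estimate insulin sensitivity and beta-cell function".

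The psychiatric and neuroendocrine sub-study has no exclusion of its own. Section 7.2.2.3 lists an ACTH challenge and "Serial collection of passive drool saliva samples for evaluation of cortisol concentrations".

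On balance between the groups, Section 7.2 says "Participants with and without Long-COVID will be age- and gender-matched where possible". On available data, Section 7.1.2.2 collects "menstrual cycle, pregnancy and lactation status (for female participants only", and Section 7.1.2.8 includes a urine "pregnancy test for woman of reproductive potential".

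**The concern.** The exploratory objective compares specialised measurements between participants with Long-COVID and controls from the same cohorts. A condition unrelated to COVID-19 that changes those measurements adds variance and, if it falls unevenly, shifts the difference. Pregnancy is such a condition for insulin sensitivity, insulin secretion and cortisol.

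Elsewhere the protocol removes conditions of this kind by eligibility. Diabetes is excluded from the glucose sub-study; smoking, household biomass exposure and earlier tuberculosis are excluded from the respiratory one. Pregnancy is not treated in the same way where glucose and cortisol are the outcomes. Each sub-study takes at most 30 people per cohort, so a single unusual participant carries visible weight in a within-cohort contrast.

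**Working it through.** **Reading the text.** The places that could close the gap are these:

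- Main-study exclusions (5.3.2): none concerns pregnancy. Exclusion 5 is investigator discretion about completing the baseline assessments.
- Sub-study exclusions (5.4.2): pregnancy appears once, limited to the respiratory sub-study. Criteria 6 and 7 could catch a pregnant woman known to have diabetes, but not one without it.
- Sections 7.2.2.3 and 7.2.2.6: no pregnancy criterion.
- Matching (7.2): age and gender, where possible.
- Confounders named in 9.2.2: vaccination, repurposed drugs, and undisclosed vaccination or prior infection. Pregnancy is not named, but the list is open.

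Nothing shown in the protocol closes the gap.

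**Scale.** The protocol gives no sample size calculation or relevant figure to reproduce. Its only number used here is the cap of 30 per cohort per sub-study, so 4 × 30 = 120 at most. Everything else is an assumption:

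- share of women (w) 60–70%
- share of those women of reproductive age (r) 60–70%
- share of those pregnant (p) 3–7%
- shift in the outcome due to pregnancy (d) 1–2 SD
- a 1:1 split of cases and controls, giving 15 per group within a cohort and 60 per group pooled. The synopsis refers only to a requisite ratio for each sub-study.

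Expected pregnant participants = 120 × w × r × p:

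- low: 120 × 0.6 × 0.6 × 0.03 = 1.3
- middle: 120 × 0.6 × 0.6 × 0.05 = 2.2
- high: 120 × 0.7 × 0.7 × 0.07 = 4.1

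As a wider check, let 0.5% to 5% of all participants be pregnant. Then 0.6 to 6 are expected among 120, and the chance of at least one, 1 − (1 − share)^120, is 45% to 99.8% (70% at a share of 1%, 91% at 2%).

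Shift in one group's mean when k pregnant women all fall on one side = k × d / n. Standard error of the difference = √(2/n) in SD units.

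| n per group | k | shift, d = 1 | shift, d = 2 | standard error |
|---|---|---|---|---|
| 15 | 1 | 0.07 | 0.13 | 0.37 |
| 15 | 2 | 0.13 | 0.27 | 0.37 |
| 60 | 2 | 0.03 | 0.07 | 0.18 |

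Two in the same small group is uncommon. Spreading 1.3 to 4.1 women over eight groups (four cohorts, cases and controls) gives a mean of 0.16 to 0.51 per group. The Poisson chance of two or more, 1 − e^(−m)(1 + m), is then about 1% to 9% for a given group.

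Added variance = q(1 − q)d², where q is the pregnant share of the group. One woman in 15 adds (1/15)(14/15) = 0.06 of the original variance at d = 1, and four times that, 0.25, at d = 2. Over all 120, q runs from 1.3/120 = 0.011 to 4.1/120 = 0.034, which adds about 1% (q = 0.011, d = 1) to 13% (q = 0.034, d = 2).

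**The case against.** The synopsis and Section 5.4.2 agree, so there is no contradiction. Section 5.5 describes the cohorts as real-life ones, and among the sub-studies CT is listed only for the respiratory one. The limit may therefore be deliberate and concern CT rather than confounding; the protocol gives no reason. This stands as an explanation of the wording, but it does not answer the effect on the OGTT and cortisol outcomes.

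The Glucose Metabolism and the Psychiatric and Neuroendocrine Sub-Study Plans are cited but not shown and could add a criterion; criterion 2 already relies on a sub-study plan for a definition. Exploratory analyses are left to the SAP. This also stands, and the recommendation is conditional on it. Even so, who enters the random draw is fixed by the protocol itself.

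A reader might infer that the Long-COVID differences will be systematically biased. The documents do not support that. Systematic bias needs pregnancy to be associated with Long-COVID status, and no figure shows that it is. Fatigue and dyspnoea are listed in Section 2.2 as common Long-COVID symptoms and can also occur in pregnancy, so some association is possible. However, the same section calls the diagnosis one of exclusion, and random selection with age and gender matching leaves mainly chance imbalance.

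A reader might also infer that the pregnancy data will be ignored. No section says so: the team reviews baseline data before selection, and the confounder list is open. Nor do the documents support extending the point to the cardiac or sleep sub-studies.

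**Conclusion.** The gap is real as the protocol is written: pregnant women can be drawn into the glucose metabolism and the psychiatric and neuroendocrine sub-studies, and the stated matching does not balance pregnancy. It is minor. The likely result is a little extra variance, with possible distortion of a single cohort's contrast by a fraction of its standard error (0.07/0.37 = 0.2 to 0.27/0.37 = 0.7). Pooled, the shift from two women on one side is at most 0.07/0.18 = 0.4 of a standard error.

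These sizes rest wholly on the assumed pregnancy share, effect size and 1:1 split. That pregnancy alters these outcomes is general physiology rather than something the protocol states. Only exploratory comparisons are affected. This is a cheap improvement, not a flaw that threatens the study.

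**What to change.** Unless the two sub-study plans already deal with it, choose one of the following:

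- In the synopsis and Section 5.4.2, extend criterion 1 to the random draw for the glucose metabolism and the psychiatric and neuroendocrine sub-studies, using the pregnancy history and urine test already collected at baseline.
- Leave eligibility as it is, and state that women pregnant at measurement are left out of the OGTT and cortisol case-control comparisons. This keeps them in the questionnaires, interview and home visit. Because the schedule allows sub-study visits up to Day 180, baseline status may be out of date, so status should be confirmed at the sub-study visit.

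The first option costs one phrase in two places; the second costs one sentence and one question at the visit. Either way a few eligible women are lost from the draw or from those comparisons, and the affected results say nothing about pregnancy. The expected numbers could not support a conclusion about pregnancy in any case.
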